9.3 Screening /Visit 1 (-30 to -1 days)

A patient who signs the informed consent document will be considered a study Subject. A Subject who withdraws from the study prior to randomization will not count toward the study's sample size. Potential participants will be screened for eligibility against **Table 1**.

Once the informed consent form is signed, the Subject is assigned a study number. The Subject number is comprised of the 2-digit site number followed by a consecutively assigned 3-digit Subject number that starts with 001. For example, the first screened Subject for site 01 will be assigned study number 01-001. The Subject number is the identification number used on CRFs and other study documents throughout the study. In the event a Subject withdraws from the study, their Subject number cannot be reassigned to any other Subject.

The Investigator, or designee, will document the Subject's medical history, demographic information, obtain vital signs and complete an assessment of the intended treatment areas and concomitant medications/concurrent procedures. Subjects will be asked to bring all prescription opioid bottles to all study follow-up visits. A pill count will be completed by the study coordinator, or designee.

Once a Subject has been determined to meet all inclusion and none of the exclusion criteria, the Subject will complete the following:

Assessments:

- NRS for Pain when standing from a seated position in target knee
- KOOS JR. (English version 1.0)

|

[REDACTED]

Physical Performance Measures in the following order:

- Timed Get Up and Go Test

Subjects may be complete Screening / Visit 1 and iovera[°] Treatment / Visit 2 on the same day.

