9.7 Study Follow Up

Study-related follow-up visits occur at the investigational site at, 72 Hours (Visit 4) Post-TKA as well as Week 2 (Visit 5), Week 6 (Visit 6), and Week 12 (Visit 7) Post-TKA. The study's schedule of assessments is shown in Table 2.

Follow Up Visit 4 (72 hours \pm 24 hours post op) - Phone Call

Visit 4 (72 Hours Post-TKA) will occur via a phone follow-up. No physical performance measures will be collected at these visits. Subjects will self-report the amount of opioids used. Subjects will report the NRS Pain Scores, answer the KOOS Jr. questions and report any AEs if present.

[figure not shown]
Follow Up Visit 5 (2 Weeks; \pm 3 Days Post Op), and Visit 6 / 6 Weeks Post-op (6 weeks; \pm 5 Days Post-Op)

Subjects will be evaluated and data collected per the schedule of events. Any changes in concomitant medications/concurrent procedures will be documented. Any anticipated observations, adverse events, adverse device effects and/or SAE/UADE/USADE will be assessed and documented. Photographs may be taken of the treatment area.

The Subject will complete a KOOS JR. questionnaire and NRS for Pain when standing from a seated position for all follow-up visits. The Subject will also complete a [REDACTED] [REDACTED] will answer Satisfaction questions at Visit 6.

The subject will complete the Physical Performance Measures for Visit 5, 6 and 7 in the following order under supervision of the investigator or designee:

- ! [REDACTED]
- Time Get-Up and Go

Subjects will be asked to bring all prescription opioid bottles to all study follow-up visits. A pill count will be completed by the study coordinator, or designee, and opioid medication will be returned to subjects.

Follow Up Visit 7 (12 Weeks; \pm 7 days Post-Op)

Subjects will be evaluated and data collected per the schedule of events. Any changes in concomitant medications/concurrent procedures will be documented. Any anticipated

observations, adverse events, adverse device effects and/or SAE/UADE/USADE will be assessed and documented. Photographs may be taken of the treatment area.

The Subject will complete a KOOS Jr. questionnaire, NRS for Pain when standing from a seated position. The Subject will also complete a [REDACTED] will answer Satisfaction questions.

The subject will complete the Physical Performance Measures in the following order under supervision of the investigator or designee:

- Get up and Go Test

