10.5 Handling of Dropouts or Missing Data

Missing data for the primary effectiveness endpoint and the first secondary effectiveness endpoint will be imputed using multiple imputation methods. First, the relatively uncommon, non-monotone missing data will be imputed using the MCMC option of SAS® PROC MI. For example, for the primary effectiveness endpoint, the imputation model will include a term for treatment and the pill counts at visits 4, 5, and 6. Second, the monotone missing values will be imputed using the chained equation method by SAS® PROC MI option MONOTONE REG. For each subject within each imputed dataset, the value of the endpoint will then be determined. The imputed data sets will each be analyzed as specified in Sections 10.4.1 and 10.4.2, and the results will be summarized using PROC MIANALYZE.

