### **3.4 Determination of Sample Size**

The sample size was determined based on the primary effectiveness endpoint, the cumulative consumption of opioids from the time of hospital discharge to 6 weeks post-TKA Surgery. Opioid consumption will be converted to morphine equivalents, and subject consumption will be verified by pill count at follow-up visits. The cumulative morphine equivalent will be divided by the number of days to provide the Total Daily Morphine Equivalent (TME) for the subject. Let  $\mu_{1,Active}$  and  $\mu_{1,SOC}$  denote the true mean TMEs for the active and standard of care treatments, respectively. The required sample size was determined based on providing at least 80% power for the primary effectiveness endpoint using a one-sided, two-independent sample, Satterthwaite t-test to test for superiority of iovera treatment to Standard of Care treatment, with a significance level of 0.025, assuming a 1:1 allocation to treatment, a true treatment effect ( $\mu_{1,Active} - \mu_{1,SOC}$ ) of -12.0 mg, and true standard deviations of 18.2 mg and 26.0 mg, for the iovera and Standard of Care treatments, respectively. Based on these specifications, the required sample size is 57 subjects per treatment group, for a total of 114 subjects. To account for a small number of subjects withdrawing early or not having data available for the analysis of the primary effectiveness endpoint, the required sample size was increased to 120 randomized subjects (approximately 60 Active Treatment subjects and 60 Standard of Care Treatment subjects).

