## 8.0 EFFECTIVENESS ANALYSES

### 8.1 Primary Effectiveness Endpoint

The primary effectiveness endpoint is the cumulative consumption of opioids from the time of hospital discharge to 6 weeks post-TKA Surgery. Opioid consumption will be converted to morphine equivalents (see Appendix 2 for conversion factors), and subject consumption will be verified by pill count at follow-up visits. The cumulative morphine equivalent will be divided by the number of days to provide the Total Daily Morphine Equivalent (TME) for the subject.

The difference in the mean TMEs between the two treatment groups will be calculated as Standard of Care TME mean – Active TME mean, such that a positive difference indicates that the Standard of Care Treatment group had a larger mean TME than the Active Treatment group, while a negative difference indicates the opposite. A positive difference between the two treatment groups reflects a positive outcome for the study.

Let  $\mu_{1,Active}$  and  $\mu_{1,SOC}$  denote the true mean TMEs for the active and standard of care treatments, respectively. Then the null and alternative hypotheses for the primary effectiveness endpoint are as follows:

$$H_0: \mu_{1,Active} \geq \mu_{1,SOC}$$

$$H_1: \mu_{1,Active} < \mu_{1,SOC}$$

Missing data for this endpoint will be imputed using multiple imputation methods. First, the relatively uncommon, non-monotone missing data will be imputed using the MCMC option of SAS® PROC MI. For this endpoint, the imputation model will include a term for treatment and the pill counts at visits 4, 5, and 6. Second, the monotone missing values will be imputed using the chained equation method by SAS® PROC MI option MONOTONE REG. For each subject within each imputed dataset, the value of the endpoint will then be determined. The imputed data sets will each be analyzed to obtain the difference in means between treatments and the corresponding standard error, and the results will be summarized using PROC MIANALYSE. A one-sided t-test will be used to test the null hypothesis. The Primary Effectiveness Study Objective will be met if this t-test is statistically significant using a  $\alpha = 0.025$  level of statistical significance.

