Let  $\mu_{2,\text{Active}}$  and  $\mu_{2,\text{SOC}}$  denote the true mean AUC/time based on the Change from Baseline in KOOS JR. score from the Baseline visit through the six-week visit for the active and standard of care treatments, respectively. Then the null and alternative hypotheses for the test for non-inferiority for this endpoint are as follows:

$$H_0: \mu_{2,\text{SOC}} - \mu_{2,\text{Active}} \geq \delta$$

$$H_1: \mu_{2,SOC} - \mu_{2,Active} < \delta,$$

where the non-inferiority margin  $\delta=14$ .

Missing KOOS JR. data will be imputed using multiple imputation methods. First, the relatively uncommon, non-monotone missing data will be imputed using the MCMC option of SAS® PROC MI. The imputation model will include a term for treatment and the KOOS JR. score at visits 1, 4, 5, and 6. Second, the monotone missing values will be imputed using the chained equation method by SAS® PROC MI option MONOTONE REG. For each subject within each imputed dataset, the value of the endpoint will then be determined. The imputed data sets will each be analyzed to obtain the difference in means between treatments and the corresponding standard error, and the results will be summarized using PROC MIANALYZE (with THETA0=14, the non-inferiority margin, in the PROC MIANALYZE statement). The null hypothesis will be tested using a one-sided t-test. One of the secondary objectives of the study is to show that, over the 6-week post-TKA period, the Active Treatment group has similar levels of pain and functioning as compared to the Standard of Care Treatment group. This objective will be met if the t-test for non-inferiority is statistically significant using a 0.025 level of statistical significance.

There is one item in the KOOS JR. scale (Knee Twisting/Pivoting) with a large number of missing responses. Prior to undergoing multiple imputation, missing values for this item will be imputed by performing a linear regression (SAS PROC GLM) on the other 6 KOOS JR. items and imputing the Knee Twisting/Pivoting score for each patient with a missing value based on the estimated linear regression line. At baseline this imputation will be performed across treatment arms; at post-baseline time points the imputation will be performed by treatment arm.

Change in NRS for Pain scores and TUG test scores from the Baseline visit to each post-baseline visit will be calculated for each subject as:

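### The primary-endpoint imputation model omits the pain scores the trial already collects and states no by-arm fit, so pain-related loss can bias the opioid difference; the effect is small at the planned 5% loss and can go either way

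*SAP*

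**What the plan says.** SAP 8.1 names the contents of the imputation model: "For this endpoint, the imputation model will include a term for treatment and the pill counts at visits 4, 5, and 6". SAP 5.3 and Protocol 10.5 give the same list as an example; the protocol's words are "for the primary effectiveness endpoint, the imputation model will include a term for treatment and the pill counts at visits 4, 5, and 6". After an MCMC step for non-monotone gaps, "the monotone missing values will be imputed using the chained equation method by SAS® PROC MI option MONOTONE REG". Neither document states a BY statement or a treatment interaction for this endpoint.

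The schedules of assessments (Protocol Table 2, SAP Table 1) place NRS and KOOS JR. at Screening and at Visits 4, 5 and 6. Protocol 9.3 lists at Screening "NRS for Pain when standing from a seated position in target knee". For the 72-hour telephone contact, Protocol 9.7 says "Subjects will report the NRS Pain Scores, answer the KOOS Jr. questions and report any AEs if present", and the same call collects self-reported opioid use. SAP 3.4 assumes "true standard deviations of 18.2 mg and 26.0 mg, for the iovera and Standard of Care treatments, respectively".

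Protocol 10.7 leaves sensitivity analyses to the SAP. SAP 8.1 adds only a Per Protocol analysis and one that excludes adverse-event discontinuations. Neither varies the missing-data assumption.

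**The concern.** Multiple imputation corrects for selective loss only through variables in the model. Pain plausibly drives both later opioid use and the decision to leave an unblinded trial. The listed model has two gaps.

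- **No count at all.** Randomisation is at Screening, up to 30 days before surgery, and all randomised patients are in the ITT population. For someone who leaves before the 72-hour call, treatment arm is the only predictor, so the imputed values are random draws around that arm's mean.
- **Lost after Visit 4 or 5.** The patient's own earlier counts are used, but the pain reported at that contact is not.

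As written, a single treatment term also implies one slope and one residual variance for both arms, while the planned variances differ by a factor of (26.0/18.2)² = 2.04.

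At stake is the primary mean difference and its one-sided 0.025 test. Loss need not be alike in the two arms: Protocol 9.10 allows withdrawal for needing prohibited treatment, and Protocol 9.6 restricts local infiltration in the iovera arm only.

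**Working it through.** **Inputs from the SAP (3.4).** Difference 12.0 mg; SDs 18.2 (iovera) and 26.0 (standard of care, SOC); 57 per arm, raised from 114 to 120 in total, so planned loss is 6/120 = 5%.

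**Assumptions not in the documents.** Correlation ρ of pain with daily morphine equivalent (TME) 0.3 to 0.5, and the same with Visit 4 use; correlation c of Visit 4 use with TME 0.5 to 0.7; log-odds of loss +1 per SD of pain; loss 5% or 15%. In one-arm cases the other arm loses the same share at random.

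**1. The plan's own figure.** n = (1.960 + 0.842)² × (18.2² + 26.0²)/12.0² = 7.85 × 1007.24/144 = 54.9, so 55 by the normal approximation and 56 with the Satterthwaite t. The stated 57 is consistent with this. Power is 80.7% at 57 and 82.7% at 60 per arm.

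**2. No count.** Error in an arm's mean = f × ρ × g × SD, where f is the share lost and g is the gap in mean pain, in SDs, between lost and retained patients. Integrating the loss model over a normal distribution gives g = 0.942 at 5% and 0.884 at 15%. Example, SOC only, ρ = 0.5, 5% loss: 0.05 × 0.5 × 0.942 × 26.0 = 0.61 mg/day. If both arms lose patients alike, the SD is replaced by 26.0 − 18.2 = 7.8.

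**3. Visit 4 use known.** The patient's own count recovers a fraction c, so multiply by (1 − c). Example: 0.61 × (1 − 0.5) = 0.31.

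Bias in SOC − iovera, mg/day (plus favours iovera):

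| Pain-related loss | 5%, no count | 5%, Visit 4 known | 15%, no count | 15%, Visit 4 known |
|---|---|---|---|---|
| SOC only | −0.37 to −0.61 | −0.11 to −0.31 | −1.03 to −1.72 | −0.31 to −0.86 |
| iovera only | +0.26 to +0.43 | +0.08 to +0.21 | +0.72 to +1.21 | +0.22 to +0.60 |
| both alike | −0.11 to −0.18 | −0.03 to −0.09 | −0.31 to −0.52 | −0.09 to −0.26 |

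A separate large-sample simulation (400,000 per arm, loss driven by Screening pain) gave similar no-count values at 5% loss: −0.40 to −0.66, +0.28 to +0.46 and −0.10 to −0.19. Loss after Visit 5 gave at most 0.07. Loss unrelated to pain, run at 10%, gave about 0.01.

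**4. Against the standard error.** √((18.2² + 26.0²)/60) = 4.10 mg. With loss in iovera only at 5%, 0.21/4.10 = 0.052 and 0.43/4.10 = 0.105. The one-sided error is then 1 − Φ(1.96 − 0.052) = 2.8% and 1 − Φ(1.96 − 0.105) = 3.2%. At 15% loss, 0.60 and 1.21 mg give 3.5% and 4.8%. These ignore the extra imputation variance, so they err slightly high.

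**5. What the remedy recovers.** From that simulation, no count, 5% loss, ρ = 0.5:

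| Pain-related loss | As listed | + Screening pain, common slope | + Screening pain, by arm |
|---|---|---|---|
| both alike | −0.19 | −0.19 | 0.01 |
| SOC only | −0.66 | −0.11 | −0.01 |
| iovera only | 0.46 | −0.10 | 0.00 |

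The pain slope scales with the arm's SD, so a common slope leaves the both-alike bias in place. The by-arm column is a best case, because loss there depends only on Screening pain.

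If 72-hour pain drives loss, the result depends on whether Visit 4 took place. With Visit 4 use and pain known, adding pain by arm leaves about 0.02 mg/day. For patients lost before Visit 4, Screening pain recovers little. If it correlates 0.4 with 72-hour pain and relates to use only through it, the share removed is 0.4 × 0.4 = 0.16, so 0.61 falls only to 0.51.

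**The case against.** The strongest reply is that this is a small matter at the expected loss, and much of that stands. A reader might go further than the documents allow in five ways.

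- **That early leavers are all filled with their arm's average.** Only patients with no count depend on the arm alone, and they receive random draws. The common slope plays no part for them.
- **That a patient can have 72-hour pain on record but no use.** One call collects both, and the SAP counts Visit 4 among the pill counts. The pattern would arise mainly if the self-report were not accepted as a count. Error rates built on it do not describe this design.
- **That the plan tilts towards iovera.** Loss concentrated in SOC works against the device, by more per patient because that SD is larger.
- **That the KOOS JR. model sets a standard the primary model breaks.** SAP 8.2 says "The imputation model will include a term for treatment and the KOOS JR. score at visits 1, 4, 5, and 6", but the Visit 1 score is part of that change-from-baseline endpoint, and no Screening pill count is scheduled. The rule that "at post-baseline time points the imputation will be performed by treatment arm" concerns a single questionnaire item.
- **That a common slope is prescribed.** It is inferred from the absence of a BY statement or interaction, and the text does not exclude either.

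It is also fair to say that a long auxiliary list would be a poor trade with about 60 patients per arm. None of this supplies the missing pain scores, or a sensitivity analysis for the missing-data assumption.

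**Conclusion.** The concern holds in a limited form. The listed model leaves out information on pain that the trial already has and, as written, implies the same slope and residual variance in both arms. If loss follows pain, the primary difference can be biased. Direction and size depend on how many patients are lost, when, and from which arm.

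At the planned 5% loss the bias is at most about 0.3 mg/day with Visit 4 use known (0.3/12 = 2.5% of the planned effect) and 0.1 to 0.7 mg/day with no count (up to about 6%). At 15% loss the upper values are about 0.9 (7.5%) and 1.7 mg/day (14%).

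All of these rest on the assumed correlations and loss model. The documents give no evidence on how pain relates to loss, so they support saying that bias is possible, not that it will occur. The change is worth making because it is cheap, not because the primary result is in serious doubt.

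**What to change.** In SAP 5.3 and 8.1:

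1. Add three auxiliary variables to the PROC MI model for the primary endpoint: one Screening pain score (NRS or KOOS JR.) and one NRS item at each of Visits 4 and 5. Name the item in advance. At 72 hours the 7-day recall item reaches back before surgery, so the current-pain item is the cleaner choice there.
2. Run PROC MI separately by treatment arm. Leave the pooled test of the difference in means as it is.
3. Add a delta-adjusted (tipping-point) analysis, with the shift set separately by arm, reporting where the one-sided result crosses 0.025. This is needed because Screening scores recover little for patients lost before Visit 4 when later pain drives the loss. With 5% imputed in one arm, a shift of 20 mg/day moves the difference by 0.05 × 20 = 1 mg/day.
4. Record the change in SAP 3.5, since Protocol 10.5 gives the present list.

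Cost: a few sentences, no new data, and more parameters. With three counts and three scores, each arm's multivariate normal model has 6 + 6×7/2 = 27 parameters, against 3 + 3×4/2 = 9 for the counts alone. Adding both NRS items and KOOS JR. at Screening and Visits 4 to 6 (12 scores) would need 15 + 15×16/2 = 135, on about 60 patients per arm. The list should therefore stay short. Visit 6 scores add little, because they will often be missing when the Visit 6 count is.

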## 8.2 Secondary Effectiveness Endpoints

The secondary effectiveness endpoints are as follows:

1. AUC/time (see definition of AUC/time below) based on Changes from Baseline in KOOS JR. Scores through 6 weeks post-TKA.  
KOOS JR. Scores range from 0 (total knee disability) to 100 (perfect knee health).
2. AUC/time based on Changes from Baseline through 6 weeks post-TKA in NRS for Pain (both pain in the last 7 days and pain right now)  
NRS Pain ratings range from 0 (no pain) to 10 (worst pain imaginable).
3. AUC/time based on Changes from Baseline through 6 weeks post-TKA in Timed Get Up and Go (TUG) test.  
The TUG test measures, in seconds, the time it takes to raise from sitting, walk 10 feet, turn around, walk back and sit back down.

Change in KOOS JR. scores from the Baseline visit to each post-baseline visit will be calculated for each subject as:

$$\text{Change in KOOS JR. score} = \text{Post-Baseline Visit KOOS JR. score} - \text{Baseline Visit KOOS JR. score},$$

such that a positive value indicates an increase in the KOOS JR. score, while a negative value indicates a decrease. The first and key secondary effectiveness endpoint, AUC/time based on Changes from Baseline in KOOS JR. scores through 6 weeks post-TKA, is the area under the curve (AUC) of Change in KOOS JR. scores from the Baseline visit through the 6-week visit divided by the number of days from TKA until the 6-week visit. AUC will be calculated using the trapezoidal rule and the changes in the KOOS JR. score at the following time points: Baseline (change=0), 72 hours, 2 weeks, and 6 weeks post-TKA. Scoring instructions for the KOOS JR. English Version 1.0 are provided in Appendix 1.

The difference in mean AUC/time between the two treatment groups will be calculated as the mean Active AUC/time – the mean Standard of Care AUC/time, such that a positive difference indicates that the Active Treatment group had a larger mean AUC/time based on Change in KOOS JR. score than the Standard of Care Treatment group, while a negative value indicates the opposite. Because a positive Change in the KOOS JR. score is indicative of pain relief, a positive difference between treatment groups reflects a positive outcome for this endpoint.

Let  $\mu_{2,\text{Active}}$  and  $\mu_{2,\text{SOC}}$  denote the true mean AUC/time based on the Change from Baseline in KOOS JR. score from the Baseline visit through the six-week visit for the active and standard of care treatments, respectively. Then the null and alternative hypotheses for the test for non-inferiority for this endpoint are as follows:

$$H_0: \mu_{2,\text{SOC}} - \mu_{2,\text{Active}} \geq \delta$$

$$H_1: \mu_{2,SOC} - \mu_{2,Active} < \delta,$$

where the non-inferiority margin  $\delta=14$ .

Missing KOOS JR. data will be imputed using multiple imputation methods. First, the relatively uncommon, non-monotone missing data will be imputed using the MCMC option of SAS® PROC MI. The imputation model will include a term for treatment and the KOOS JR. score at visits 1, 4, 5, and 6. Second, the monotone missing values will be imputed using the chained equation method by SAS® PROC MI option MONOTONE REG. For each subject within each imputed dataset, the value of the endpoint will then be determined. The imputed data sets will each be analyzed to obtain the difference in means between treatments and the corresponding standard error, and the results will be summarized using PROC MIANALYZE (with THETA0=14, the non-inferiority margin, in the PROC MIANALYZE statement). The null hypothesis will be tested using a one-sided t-test. One of the secondary objectives of the study is to show that, over the 6-week post-TKA period, the Active Treatment group has similar levels of pain and functioning as compared to the Standard of Care Treatment group. This objective will be met if the t-test for non-inferiority is statistically significant using a 0.025 level of statistical significance.

There is one item in the KOOS JR. scale (Knee Twisting/Pivoting) with a large number of missing responses. Prior to undergoing multiple imputation, missing values for this item will be imputed by performing a linear regression (SAS PROC GLM) on the other 6 KOOS JR. items and imputing the Knee Twisting/Pivoting score for each patient with a missing value based on the estimated linear regression line. At baseline this imputation will be performed across treatment arms; at post-baseline time points the imputation will be performed by treatment arm.

Change in NRS for Pain scores and TUG test scores from the Baseline visit to each post-baseline visit will be calculated for each subject as:

$$\text{Change score} = \text{Baseline Visit score} - \text{Post-Baseline Visit score},$$

such that a positive value indicates a decrease in the score (which is a positive outcome), while a negative value indicates an increase (which is a negative outcome). AUC/time for these endpoints will be calculated in the same way described above for KOOS JR.

Each secondary effectiveness endpoint will be summarized by treatment using descriptive statistics. For each treatment, the null hypothesis that the true mean AUC/time equals zero will be tested using a paired t-test. Ninety-five percent confidence intervals based on the t-distribution for the true mean AUC/time for each treatment and for the true difference in these means between treatments will be provided. For the second and third secondary effectiveness endpoints, a one-sided, two-sample t-test will be used to test the null hypothesis that the iovera mean is less than or equal to the Standard of Care mean versus the alternative hypothesis that the iovera mean is greater than the Standard of Care mean. In addition, for each secondary effectiveness endpoint, the initial result (e.g., KOOS JR. score at 6-weeks post-TKA), as well as the Change from Baseline value, will be summarized by treatment group at each visit at which data for the endpoint are collected using descriptive statistics, together with 95% confidence intervals for the mean based on the t-distribution. The estimated difference in the mean change from baseline between the two treatment groups and a 95% confidence interval based on the t-distribution for the true difference in these means between the two treatments will also be provided.

The fixed sequential testing procedure will be used for the comparison of the two treatments with respect to the first (and key) secondary effectiveness endpoint. Therefore, for this endpoint, the analysis comparing the two treatments will be formally conducted only if the analysis for the primary effectiveness endpoint yields a statistically significant result. For informational purposes, however, the results of the analyses (i.e., p-value) will be presented regardless of the results for the primary effectiveness endpoint.

These analyses will be performed for the ITT Population.

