## Appendix 1:

# KOOS, JR SCORING INSTRUCTIONS

The KOOS, JR was developed from the original long version of the Knee injury and Osteoarthritis Outcome Score (KOOS) survey using Rasch analysis. The KOOS, JR contains 7 items from the original KOOS survey. Items are coded from 0 to 4, none to extreme respectively.

KOOS, JR is scored by summing the raw response (range 0-28) and then converting it to an interval score using the table provided below. The interval score ranges from 0 to 100 where 0 represents total knee disability and 100 represents perfect knee health.

Table for converting raw summed scores to interval level scores from 0 (total knee disability) to 100 (perfect knee health)

Raw summed score (0-28)	Interval score (0 to 100 scale)
0	100.000
1	91.975
2	84.600
3	79.914
4	76.332
5	73.342
6	70.704
7	68.284
8	65.994
9	63.776
10	61.583
11	59.381
12	57.140
13	54.840
14	52.465
15	50.012
16	47.487
17	44.905
18	42.281
19	39.625
20	36.931
21	34.174
22	31.307
23	28.251
24	24.875
25	20.941
26	15.939
27	8.291
28	0.000

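### The heavily missing KOOS JR. twisting item is filled once from a regression line before multiple imputation, so its uncertainty is dropped and the filled sums have no row in the scoring table; the likely effect on the test is small

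*SAP*

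**What the plan says.** The key secondary endpoint is AUC/time of change in KOOS JR. through 6 weeks, tested for non-inferiority with a margin of 14. The success rule in SAP 8.2 is: "This objective will be met if the t-test for non-inferiority is statistically significant using a 0.025 level of statistical significance".

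SAP 8.2 describes two layers of imputation for this endpoint.

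- **Item layer.** "There is one item in the KOOS JR. scale (Knee Twisting/Pivoting) with a large number of missing responses". Before multiple imputation, PROC GLM regresses this item on the other six, and each gap is closed by "imputing the Knee Twisting/Pivoting score for each patient with a missing value based on the estimated linear regression line". On grouping: "At baseline this imputation will be performed across treatment arms; at post-baseline time points the imputation will be performed by treatment arm".
- **Score layer.** Multiple imputation then follows, using overall scores: "The imputation model will include a term for treatment and the KOOS JR. score at visits 1, 4, 5, and 6". On the analysis step: "The imputed data sets will each be analyzed to obtain the difference in means between treatments and the corresponding standard error". PROC MIANALYZE combines the results.

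Appendix 1 codes items 0 to 4 and scores the instrument by "summing the raw response (range 0-28) and then converting it to an interval score using the table provided below". The table has one row for each whole number from 0 to 28.

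Protocol 10.5 specifies multiple imputation for this endpoint and no item-level single fill. SAP 3.5, on changes from the protocol, covers only how results are combined across imputed datasets. The Table 3 shell footnote mentions multiple imputation of overall scores and is silent on the item fill.

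**The concern.** The plan uses proper multiple imputation for gaps at score level, including those it calls relatively uncommon. It uses a single deterministic fill for the one item it singles out as often missing. A value on the fitted line carries no residual draw and no draw of the regression coefficients. Once it is summed into a score, PROC MI cannot tell it from an answer the patient gave. Rubin's rules can only combine variance that the imputations contain, and here they contain none from the fill. In a non-inferiority test, an understated standard error works in favour of the claim.

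The second problem is practical. A fitted item value such as 2.37 gives a raw sum with no row in Appendix 1. Two programmers could follow the SAP to the letter and report different values for the key secondary endpoint. The trial is unblinded (SAP 3.3), and the SAP's wording shows that the extent of missing responses was already known, so a choice of this kind should be fixed in writing.

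SAP 8.4 applies the 8.2 method to the 72-hour, 2-week and 12-week KOOS JR. analyses, so the same step carries over.

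**Working it through.** **Is there a figure in the plan to reproduce?** No. Neither document gives a standard error, SD, power or missing-item rate for the KOOS JR. test. The inputs taken from the documents are about 60 per arm (SAP 3.4), seven items coded 0 to 4 and the conversion table (Appendix 1), visits at day 0, 72 hours, 2 weeks and 6 weeks, the margin of 14 and the 0.025 level (SAP 8.2). The missing rate, inter-item correlation and missingness mechanism are assumptions.

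**Step 1: the lookup.** Subtract successive rows of Appendix 1.

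- Over the whole table the steps run from 2.193 (sums 9 to 10: 63.776 − 61.583) to 8.291 (sums 27 to 28).
- Between sums 4 and 23 they run from 2.193 to 3.056 (sums 22 to 23: 31.307 − 28.251).
- Rounding to the nearest row instead of interpolating moves a score by at most half a step: 3.056 / 2 = 1.53 points between sums 4 and 23, and up to 8.291 / 2 = 4.15 at the extreme end.

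In simulation, 98 to 100% of filled values were non-integer. The share outside 0 to 4 was 0.2 to 2.8% at 20 to 60% missing; under other assumptions, including much heavier missingness, it reached 21%. In the arm difference, rounding instead of interpolating made a change with SD 0.10 to 0.16 points, and always rounding down instead of up made one with SD 0.27 to 0.34. The standard error in those runs was 2.2 to 2.6.

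**Step 2: the standard error.** Simulated trials had 60 per arm, the AUC/time endpoint as defined, and the item deleted completely at random. It was filled as in SAP 8.2 (pooled at baseline, by arm afterwards), with non-integer sums interpolated. There were about 22,000 to 26,000 trials per cell. The first figure in each cell is the reported standard error divided by the estimator's actual sampling SD. The second is the reported standard error divided by that from item-level stochastic multiple imputation (10 imputations, 250 trials).

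| Inter-item correlation | 20% missing | 40% missing | 60% missing |
|---|---|---|---|
| 0.3 | 1.001; 0.981 | 0.982; 0.960 | 0.976; 0.927 |
| 0.5 | 0.999; 0.988 | 0.989; 0.974 | 0.988; 0.950 |
| 0.7 | 0.994; 0.993 | 0.991; 0.986 | 0.991; 0.973 |

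With no item missing, the first ratio itself ran from 0.992 to 1.004, so differences under 1% are noise. Simulated one-sided error in either tail was 0.023 to 0.028.

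**Step 3: heavier missingness.** Further runs used correlations of 0.4 and 0.6 (1,500 to 4,000 trials per cell). At 70% missing most set-ups gave a shortfall of 0 to 3%, and one gave 5 to 6%. At 80% the shortfall was about 10 to 20%, with one-sided error of about 0.035 to 0.05.

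The reason is visible in the design. At 80% missing, 60 × 0.20 = 12 respondents per arm support seven coefficients (an intercept and six slopes), leaving 12 − 7 = 5 residual degrees of freedom. Error in those coefficients shifts all filled values in an arm together, so it does not show in the spread between patients.

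**Step 4: what a shortfall does at the margin.** If the reported standard error is a fraction f of the true one, one-sided error is 1 − Φ(1.96 f). The largest observed deficit that still passes is 14 − 1.96 × SE × f. With a true SE of 2.1 (the simulated range was 1.8 to 2.4):

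| f | One-sided error | Largest passing deficit |
|---|---|---|
| 1.00 | 0.0250 | 9.88 |
| 0.98 | 0.0274 | 9.97 |
| 0.93 | 0.0342 | 10.17 |
| 0.90 | 0.0389 | 10.30 |
| 0.80 | 0.0584 | 10.71 |

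The pass boundary moves by 10.71 − 9.88 = 0.83 points at the most severe setting, and by 0.09 points for a 2% shortfall.

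**The case against.** The best defence is that the step is harmless in practice. The item is one of seven and the other six predict it. At moderate missingness the reported standard error matches the estimator's own sampling SD to within about 2%. The endpoint is secondary and formally tested only if the primary succeeds. One sentence giving a conversion rule would make the lookup executable without removing the PROC GLM step.

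Most of this stands. A reader might infer that the key standard error is too small and the non-inferiority test anti-conservative without qualification. The documents do not support that: they say only that many responses are missing, and a material shortfall needs about 80%. Nor should the 0.93 to 0.99 ratios against proper multiple imputation be read as inflated error. They compare two procedures, whereas error depends on each standard error against its own estimator's sampling SD. A reader might also infer that rounding shifts scores by several points; that can happen only near the ends of Appendix 1.

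The defence does not make the method proper, and a conversion rule would leave the fill's uncertainty uncounted. No other section supplies the rule or discloses the step.

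**Conclusion.** Wrong as written, with limited impact. Three things follow from the text alone: the fill is single and deterministic, its uncertainty never reaches PROC MIANALYZE, and Appendix 1 cannot score the resulting sums without a rule the SAP does not state. The omission from SAP 3.5 is also plain.

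The size is conditional. Assuming 60 per arm, inter-item correlations of 0.3 to 0.7 and responses missing completely at random, the standard-error shortfall is about 0 to 3% up to roughly 60 to 70% missing and about 10 to 20% at 80%. Most scores move by no more than about 1.5 points under the choice between rounding and interpolation. Against a margin of 14, neither would be likely to change the conclusion alone unless the result lay close to the margin.

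If patients skip the item because they cannot twist or pivot, bias could matter more than the standard error. That was not simulated, and the documents do not give the reason for the missing answers.

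**What to change.** Delete the PROC GLM step and impute the item inside the multiple imputation:

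1. Use PROC MI with FCS and predictive mean matching (REGPMM), so that imputed responses are whole numbers from 0 to 4. Do not use MONOTONE for this item, because gaps in one item across visits are generally non-monotone.
2. Include treatment (or impute by arm), the other six items at that visit, and KOOS JR. data from other visits. Keep the model small if respondents are few.
3. Score each imputed dataset with Appendix 1.
4. Impute visits with the whole KOOS JR. missing at score level, as now planned, within each of those datasets. Then combine in PROC MIANALYZE.
5. List the change in SAP 3.5, mention item imputation in the Table 3 footnote, and report the item's missing counts by arm and visit so that readers can judge the size.

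The cost is SAP wording, a few lines of SAS and possibly a slightly wider confidence interval.
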